3. STUDY DESIGN

3.1 DESCRIPTION OF THE STUDY

Study CO39721 is a Phase Ib, open-label, multicenter, global study designed to evaluate the preliminary efficacy, safety, and pharmacokinetics of cobimetinib and atezolizumab when given to patients with $BRAF^{V600}$ WT metastatic or unresectable locally advanced melanoma who have progressed on a prior anti-PD-1 therapy. It is also designed to evaluate efficacy, safety, and pharmacokinetics of atezolizumab monotherapy in patients with $BRAF^{V600}$ WT metastatic or unresectable locally advanced melanoma who have not been previously treated. The co-primary endpoints of the study are ORR and DCR.

Approximately 102 patients with $BRAF^{V600}$ WT advanced melanoma who have progressed on a prior anti-PD-1 therapy will be enrolled in Cohorts A and B of this study (see [Figure 4](#)).

- Cohort A: Approximately 90 patients who have progressed on or after treatment with an anti-PD-1 agent will be enrolled.
- Cohort B (biopsy cohort): *Approximately* 12 patients will be enrolled in a mandatory biopsy cohort with inclusion according to the eligibility criteria specified in Section [4.1](#).

Approximately 50 patients who have not *received any prior anti-cancer treatment in the metastatic setting* will be enrolled in Cohort C.

Cohort A and B

[figure not shown]
All cycles will be 28 days in length for Cohorts A and B. Patients in Cohort A will begin dosing with cobimetinib and atezolizumab concurrently and will receive in all cycles 840 mg atezolizumab intravenous (IV) Q2W and 60 mg cobimetinib QD 21/7 (see [Figure 5](#)).

Patients in Cohort B (biopsy cohort) will also receive 60 mg cobimetinib QD 21/7 in all cycles. However, patients in this cohort will begin dosing with cobimetinib before atezolizumab and will receive 60 mg cobimetinib alone QD for the first 14 days of Cycle 1. Atezolizumab dosing (840 mg IV) will begin on Day 15, Cycle 1, and will continue thereafter at 840 mg IV Q2W. In Cycle 2 and all subsequent cycles, patients in this cohort will receive 60 mg cobimetinib QD 21/7 and 840 mg atezolizumab IV Q2W (see [Figure 6](#)).

Cohort C

[figure not shown]
All cycles in Cohort C will be 21 days in length. Patients in Cohort C will receive atezolizumab (1200 mg) Q3W (see [Figure 6](#)).

Figure 4 Study Schema

[figure not shown]

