3.1.1.2 Mandatory Biopsies (Cohort B)

Patients enrolled in Cohort B, the biopsy cohort, must have at least two (preferably three) accessible lesions that meet the requirements specified in the eligibility criteria.

Exceptions may be made if patient has only one lesion that allows multiple biopsies following discussion with Medical Monitor. One pretreatment, up to two on-treatment biopsies, and one post-progression biopsy will be performed. If more than one biopsy will be obtained from one lesion, the lesion should be large enough to permit successive biopsies ≥ 1 cm apart. Investigators are strongly encouraged to obtain two on-treatment biopsies as described below; at a minimum, the Day 10–14 biopsy should be obtained to test for possible immunologic effects of cobimetinib alone.

Patients in the biopsy cohort will undergo biopsies according to the following schedule:

- A predose biopsy will be taken before Day 1, Cycle 1. (The predose biopsy is not required if a fresh biopsy was provided during screening).
- On Day 1, Cycle 1, patients will start treatment with cobimetinib alone.
- A mandatory on-treatment biopsy will be obtained between Days 10 and 14 of Cycle 1.
- Patients will receive their first atezolizumab dose on Day 15 of Cycle 1.
- A second, optional, on-treatment biopsy will be obtained during Cycle 2, 4–6 weeks after the first dose of atezolizumab to assess the combined effects of cobimetinib and atezolizumab.
- A mandatory, post-treatment biopsy will be obtained at the time of radiographic progression.

Patients in tumor biopsy cohorts whose tissue sample is not evaluable may receive study treatment, but these patients may be replaced for the purpose of serial biopsy assessment.

If a patient undergoes a medically indicated procedure at any time during the study that has the likelihood of yielding tumor tissue, any remaining samples or a portion of the tumor sample not necessary for medical diagnosis may be obtained for exploratory analysis. Patients must have provided specific consent in order for discarded samples from routine care to be obtained.

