3.3.1.2 Cohort B (Biopsy Cohort)

Cohort B is designed to allow assessment of the effects of cobimetinib on immune therapy. In this cohort, in Cycle 1 only, cobimetinib will be given for 14 days before initiation of atezolizumab treatment as described in Section 3.1. Biopsies obtained before treatment start and at the end of the 14-day cobimetinib monotherapy period will allow elucidation of the effects of cobimetinib on tumor immune contexture. Additional biopsies taken during the combination treatment period and at radiographic progression will support evaluation of the effects of combination treatment on the tumor micro-environment and the identification of potential mechanisms of resistance to combination therapy.

During Cycle 2 and all subsequent cycles, patients in Cohort B will receive cobimetinib 60 mg QD 21/7 and atezolizumab 840 mg IV Q2W, the same dose and schedule as in Cohort A.

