ADA=anti-drug antibody; CPK=increased creatine phosphokinase; ECHO=echocardiogram; ECOG PS=Eastern Cooperative Oncology Group performance status; eCRF=electronic Case Report Form; FU=follow-up; HBcAb=hepatitis B core antibody; HBcAg=hepatitis B core antigen; HBsAg=hepatitis B surface antigen; HBV=hepatitis B virus; HCV=hepatitis C virus; LVEF=left ventricular ejection fraction; MUGA=multiple-gated acquisition; PD=progressive disease; PK=pharmacokinetic; Q3M=every 3 months; RECIST=Response Evaluation Criteria in Solid Tumors; T3=triiodothyronine; T4=thyroxine; TSH=thyroid-stimulating hormone; WGS=whole genome sequencing; WT=wild type.

Notes: All assessments should be performed within ± 3 days of the scheduled visit, unless otherwise specified. On treatment days, all assessments should be performed prior to dosing, unless otherwise specified. On treatment days, pre-infusion laboratory samples should be drawn up to 4 hours before the start of infusion, and post-infusion laboratory samples should be drawn up to 30 minutes after the end of infusion, unless otherwise specified.

- ^a Results of standard-of-care tests or examinations performed before obtaining informed consent and within 35 days before Day 1 may be used; such tests do not need to be repeated for screening. *BRAF*^{V600} status must be known prior to performing study-specific screening assessments. The 35-day window begins at the time of the first standard-of-care screening assessment or the first study-specific screening assessment after the *BRAF*^{V600} mutation test result is available, whichever is earlier. Test results should be reviewed before study treatment is given.
- ^b Patients who discontinue study drug will return to the clinic for a treatment discontinuation visit at 30 (± 3) days. The visit at which response assessment shows PD may be used as the study discontinuation visit.
- ^c Visit not specified by the protocol. Assessments (possibly including PK sample collection) should be performed as clinically indicated.
- ^d Required follow-up information will be collected via telephone calls and/or clinic visits every 3 months until death, loss to follow-up, or study termination by the Sponsor.
- ^e Informed consent must be documented before any study-specific screening procedure is performed and may be obtained up to 35 days before initiation of study treatment.

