A subsequent mandatory biopsy will be performed between Days 10 and 14 of Cycle 1. An additional optional biopsy may be collected during Cycle 2, approximately 4–6 weeks after the first atezolizumab administration. A mandatory biopsy will be collected at the time of radiographic progression, if clinically feasible.
- ^u Days 10–14.
- ^v In Cohort B, atezolizumab will be given on Cycle 1, Day 15 and on Days 1 and 15 of all subsequent cycles. The initial dose will be delivered over 60 (\pm 15) minutes. If the first infusion is well tolerated all subsequent infusions will be delivered over 30 (\pm 10) minutes until a loss of clinical benefit. Study drug administration may be \pm 3 days from the scheduled Day 1 and 15 of each cycle.
- ^w Cobimetinib 60 mg/day by mouth will be given in a 21/7 dosing schedule. Dosing will start on Cycle 1, Day 1, 14 days before the first atezolizumab administration.

Appendix 1
Schedule of Activities (cont.)
Cohort C: Atezolizumab Monotherapy (21-Day Cycle)

Day (window)	Screening ^a	Cycle 1	Cycle 2	Cycle 3+	Treatment Discontinuation ^b	Unplanned Visit ^c	Survival FU ^d
	-35 to -1	1	1	1	30 (± 3) d after last dose		Q3M
Informed consent ^e	x						
Demographic data	x						
Medical history	x						
Vital signs ^{f, g}	x	x	x	x	x	x	
ECOG PS	x	x	x	x		x	
Weight	x	x	x	x	x		
Height	x						
Complete physical examination	x				x		
Limited physical examination		x ^h	x	x			
Hematology ⁱ	x	x	x	x	x	x	
Coagulation (INR and aPTT)	x						
BRAF ^{V600} WT mutation status	x						
PK/ADA sample for atezolizumab	See Appendix 2						
Serum samples for auto antibody tests ^j		x					
Optional WGS		x					

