Appendix 2 Schedule of Pharmacokinetic, Immunogenicity, and Biomarker Samples (cont.)

Cohort B

Visit	Timepoint	Sample Type(s)
Cycle 1, Day 15	Prior to the first infusion	Atezolizumab PK and ADA (serum)
	30 (\pm 10) minutes following the end of atezolizumab infusion	Atezolizumab PK (serum)
	Prior to cobimetinib dose 2–4 hours post cobimetinib dose	Cobimetinib PK (plasma)
Cycles 2, 3, 4, 8, 12, and 16	Prior to the first infusion	Atezolizumab PK and ADA (serum)
Cycles 1 and 2, Day 1 At time of tumor assessments (preferably within 3 days) At disease progression	Predose	Biomarker (plasma, PBMC)
Treatment discontinuation visit ^a	At visit	Atezolizumab PK and ADA (serum) Biomarker (plasma, PBMC) ^b
120 days \pm 30 days after last atezolizumab infusion	At visit	Atezolizumab PK and ADA (serum)

ADA=anti-drug antibody; PBMC=peripheral blood mononuclear cell; PK=pharmacokinetic; RECIST=Response Evaluation Criteria in Solid Tumors.

Note: Except for Day 15 of Cycle 1, all other study visits and assessments during the treatment period should be performed within \pm 3 days of the scheduled date. Study assessments may be delayed or moved ahead of the window to accommodate holidays, vacations, and unforeseen delays.

^a Patients who discontinue study drug will return to the clinic for a treatment discontinuation visit 30 (\pm 3) days after the last dose of study drug. The visit at which response assessment shows progressive disease may be used as the treatment discontinuation visit.

^b At confirmed disease progression, lack of clinical benefit, or at treatment discontinuation.

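### Cohort B: the ±3-day dosing window in Appendix 1 footnote v has no exception for the first atezolizumab dose, so it conflicts with the 14-day cobimetinib-alone lead-in

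*Combined protocol and SAP*

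**What the plan says.** Appendix 1, Cohort B footnote v, schedules atezolizumab on Cycle 1 Day 15 and on Days 1 and 15 of later cycles. It then allows study drug administration within plus or minus "3 days from the scheduled Day 1 and 15 of each cycle". Cycle 1 is not excepted.

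The other texts fix the lead-in and the order of events without any tolerance:

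- Footnote w, directly below: "Dosing will start on Cycle 1, Day 1, 14 days before the first atezolizumab administration".
- Section 3.1: Cohort B patients "will receive 60 mg cobimetinib alone QD for the first 14 days of Cycle 1".
- Section 3.3.1.2: "in Cycle 1 only, cobimetinib will be given for 14 days before initiation of atezolizumab treatment".
- Sections 3.1.1.2 and 4.2.2.2: the first atezolizumab dose is on Day 15 of Cycle 1.
- Footnote t: "A subsequent mandatory biopsy will be performed between Days 10 and 14 of Cycle 1". Section 3.1.1.2 gives the purpose: "the Day 10–14 biopsy should be obtained to test for possible immunologic effects of cobimetinib alone".

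Two notes bear on timing. The Cohort B notes in Appendix 1 say: "On treatment days, all assessments should be performed prior to dosing, unless otherwise specified". The Cohort B note in Appendix 2 sets its own ±3-day window but opens with "Except for Day 15 of Cycle 1, all other study visits and assessments during the treatment period", so it takes the Cycle 1 Day 15 visit out of that window.

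**The concern.** Footnote v is the only text that sets a dosing window for Cohort B. Its wording includes Cycle 1, and the only Cycle 1 atezolizumab dose in this cohort is the one on Day 15. The window therefore sits on the boundary between cobimetinib alone and the combination. A site that gave the first infusion on Day 12 and took the biopsy on Day 14 would comply with footnotes v and t while breaching footnote w.

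What is at stake is the meaning of one sample. A biopsy taken after an atezolizumab infusion is no longer a cobimetinib-alone sample, and the effect of cobimetinib on tumor immune contexture is a listed exploratory objective. Section 3.1.1.2 allows replacement of a patient whose tissue is not evaluable, but it does not mention tissue that is readable and mistimed. With about 6 patients in each resistance group, one such sample would be about 1 in 6 of its group.

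**Working it through.** **Inputs.** Scheduled first atezolizumab dose: Cycle 1 Day 15 (footnote v; Sections 3.1.1.2 and 4.2.2.2). Dosing window: ±3 days (footnote v). Biopsy window: Days 10 to 14 (footnote t; Section 3.1.1.2). Cobimetinib starts on Cycle 1 Day 1 (footnote w).

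**The plan's own figure.** Lead-in = first atezolizumab day − 1. As scheduled, 15 − 1 = 14 days, which agrees with footnote w and Sections 3.1 and 3.3.1.2.

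**The window as written.** The earliest dose is on Day 15 − 3 = 12 and the latest on Day 15 + 3 = 18, so there are 7 possible dose days and the lead-in runs from 11 to 17 days.

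| Shift | Dose day | Days of cobimetinib alone | Biopsy days later than the dose day |
|---|---|---|---|
| −3 | 12 | 11 | 13, 14 |
| −2 | 13 | 12 | 14 |
| −1 | 14 | 13 | none |
| 0 | 15 | 14 | none |
| +1 | 16 | 15 | none |
| +2 | 17 | 16 | none |
| +3 | 18 | 17 | none |

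**Count.** 7 dose days × 5 biopsy days = 35 permitted pairs. The dose falls on an earlier day than the biopsy in 2 + 1 = 3 of them (dose/biopsy days 12/13, 12/14 and 13/14). Same-day pairs (12/12, 13/13 and 14/14) are not counted, because the Appendix 1 note puts assessments before dosing on treatment days. The exposed biopsy days are 13 and 14, which is 2 of 5. The largest gap is 14 − 12 = 2 days.

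**After the change.** With 0 to +3 days, the dose days are 15 to 18: 4 × 5 = 20 pairs, of which 0 conflict. Late dosing never conflicts; it only lengthens the lead-in.

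**The case against.** The strongest reply is that the rest of the protocol already settles the order.

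Appendix 2 takes the Cohort B Cycle 1 Day 15 visit out of its ±3-day window. At that visit it schedules one sample before the first infusion and another 30 (±10) minutes after the infusion ends. A visit fixed on Day 15 with a sample half an hour after the infusion ties the infusion to that day in practice. The Appendix 1 table also lists the Day 10 to 14 biopsy in the Cycle 1 Day 15 column, which suggests biopsy first and dose second. Section 3.1.1.2 gives the same order, and footnote w follows directly on footnote v. The window sentence also appears in Cohort A footnote u, so it reads as a general tolerance and not as a deliberate permission to shorten the lead-in. Finally, harm needs two choices together: bringing the first dose forward, and leaving a mandatory biopsy until after it.

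Most of this stands as evidence of intent: biopsy before atezolizumab is plainly what the sponsor wants, and nothing in the documents suggests that the reverse is likely. It does not repair footnote v. The Appendix 2 exception is worded for visits and assessments, not dosing, and that note also lets assessments move for holidays and unforeseen delays. If it is nevertheless read as fixing the infusion day, footnote v contradicts one more text. The treatment-day note resolves only same-day cases. The shared wording with Cohort A, which has no lead-in, points to a sentence carried over without adaptation.

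**Conclusion.** The concern holds, as a minor point. Footnote v states a permission that conflicts with footnote w and with Sections 3.1, 3.1.1.2, 3.3.1.2 and 4.2.2.2. Taken literally, it lets the cobimetinib-alone biopsy follow the first atezolizumab infusion in 3 of 35 permitted day pairs, by no more than 2 days. The count gives every pair equal weight and says nothing about how often sites would use the allowance. It assumes that the footnote v window applies to Cycle 1 as worded, and that same-day biopsies precede the infusion.

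The design itself is sound, and its intended order is stated repeatedly. The effect is confined to a descriptive, exploratory biomarker analysis in about 12 patients. No primary endpoint, safety rule or sample size changes.

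**What to change.** In Appendix 1, Cohort B footnote v, replace the ±3-day allowance with 0 to +3 days for the Cycle 1 Day 15 dose only. Add one sentence saying that the Day 10 to 14 biopsy must be taken before the first atezolizumab infusion. Keep ±3 days for all later doses. Requiring Day 15 exactly would match the Appendix 2 exception, but it would remove late flexibility that does no harm, so 0 to +3 days is preferable.

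The cost is one clause and one sentence. No visit, procedure or patient is added, and sites lose only the option of giving a single dose up to 3 days early.

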Appendix 1 Schedule of Activities (cont.)

Cohort C: Atezolizumab Monotherapy (21-Day Cycle)

Day (window)	Screening ^a	Cycle 1	Cycle 2	Cycle 3+	Treatment Discontinuation ^b	Unplanned Visit ^c	Survival FU ^d
	-35 to -1	1	1	1	30 (\pm 3) days after last dose		Q3M
Chemistry ^k	x	x	x	x	x	x	
Tumor Assessments ^l	x	Scan assessments every 8 weeks \pm 7 days					
ECHO/MUGA scan ^m	x						
ECG (average of triplicate measurements)	x					x	
Serology ⁿ	x						
Thyroid function ^o	x	x	x	x ^o	x		
Pregnancy test ^p	x	x	x	x ^p	x	x	
Urinalysis ^q	x						
Concomitant medications ^r	x ^r	x ^r	x	x	x ^r		
Adverse events ^s	x ^s	x ^s	x	x	x ^s		x ^s
Collection of archival tissue or tumor biopsy ^t	x				x		
Biomarker blood samples		See Appendix 2					
Atezolizumab administration ^u		x	x	x			
Survival and anti-cancer therapy FU							x

Appendix 1

Schedule of Activities (cont.)

ADA=anti-drug antibody; CPK=increased creatine phosphokinase; ECHO =echocardiogram; ECOG PS= Eastern Cooperative Oncology Group performance status; eCRF =electronic Case Report Form; FU= follow-up; HBcAb= hepatitis B core antibody; HBcAg= hepatitis B core antigen; HBsAg= hepatitis B surface antigen; HBV= hepatitis B virus; HCV= hepatitis C virus; LVEF= left ventricular ejection fraction; MUGA= multiple-gated acquisition; PD= progressive disease; PK= pharmacokinetic; Q3M= every 3 months; RECIST= Response Evaluation Criteria in Solid Tumors; T3= triiodothyronine; T4= thyroxine; TSH= thyroid-stimulating hormone; WGS= whole genome sequencing; WT= wild type.

Notes: All assessments should be performed within ± 3 days of the scheduled visit, unless otherwise specified. On treatment days, all assessments should be performed before dosing, unless otherwise specified. On treatment days, pre-infusion laboratory samples should be drawn up to 4 hours before the start of infusion, and post-infusion laboratory samples should be drawn up to 30 minutes after the end of infusion, unless otherwise specified.

- ^a Results of standard-of-care tests or examinations performed before obtaining informed consent and within 35 days before Day 1 may be used; such tests do not need to be repeated for screening. *BRAF*^{V600} status must be known before performing study-specific screening assessments. The 35-day window begins at the time of the first standard-of-care screening assessment or the first study-specific screening assessment after the *BRAF*^{V600} mutation test result is available, whichever is earlier. Test results should be reviewed before study treatment is given.
- ^b Patients who discontinue study drug will return to the clinic for a treatment discontinuation visit at 30 (± 3) days. The visit at which response assessment shows PD may be used as the study discontinuation visit.
- ^c Visit not specified by the protocol. Assessments (possibly including PK sample collection) should be performed as clinically indicated.
- ^d Required follow-up information will be collected via telephone calls and/or clinic visits every 3 months until death, loss to follow-up, or study termination by the Sponsor. PK/ADA sample is required 120 days \pm 30 days after last atezolizumab infusion
- ^e Informed consent must be documented before any study-specific screening procedure is performed and may be obtained up to 35 days before initiation of study treatment.
- ^f Includes respiratory rate, heart rate, and systolic and diastolic blood pressure (after patient has been in a seated position for 5 minutes) and temperature (oral or tympanic); resting oxygen saturation may be measured at screening. Record abnormalities observed at baseline on the General Medical History and Baseline Conditions eCRF. At subsequent visits, record new or worsened clinically significant abnormalities on the Adverse Event eCRF.
- ^g Vital signs at the first atezolizumab infusion will be collected within 60 min before the infusion, every 15 (± 5) min during the atezolizumab infusion, and 30 (± 10) min after the infusion. For subsequent infusions, vital signs will be collected within 60 min before infusion and during the infusion (if clinically indicated or if symptoms occurred in the prior infusion), and 30 (± 10) min after the infusion.
- ^h Perform a limited, symptom-directed examination at specified timepoints or as clinically indicated. Record new or worsened clinically significant abnormalities on the Adverse Event eCRF. If physical examinations are assessed within 7 days of the Cycle 1, Day 1 visit, they do not have to be repeated at Day 1.

Appendix 1 Schedule of Activities (cont.)

- ⁱ Hematology includes WBC count, RBC count, hemoglobin, hematocrit, platelet count, reticulocyte count, differential count (neutrophils, eosinophils, basophils, monocytes, and lymphocytes).
- ^j Includes anti-nuclear antibody, anti-double-stranded DNA, circulating anti-neutrophil cytoplasmic antibody, and perinuclear anti-neutrophil cytoplasmic antibody.
- ^k Chemistry panel (serum or plasma) includes sodium, potassium, chloride, bicarbonate (or total carbon dioxide), BUN or urea, creatinine, total protein, magnesium, phosphorus, calcium, total and direct bilirubin, ALP, ALT, AST, CPK, LDH, uric acid; albumin, non-fasting glucose (fasting blood glucose after a minimum 8-hour fast, at screening only), lipids, (Fasting lipids: total cholesterol, LDL cholesterol, and triglycerides after a minimum 8-hour fast, at screening only).
- ^l Tumor assessments will continue until disease progression per RECIST v1.1, loss of clinical benefit (patients who continue treatment after disease progression according to RECIST v1.1), consent withdrawal, study termination by the Sponsor, or death, whichever occurs first. At the investigator's discretion, tumor assessments may be repeated at any time if disease progression is suspected. Patients who discontinue treatment for reasons other than disease progression (e.g., toxicity) will continue scheduled tumor assessments until disease progression, withdrawal of consent, study termination by Sponsor, or death, whichever occurs first.
- ^m All patients will undergo evaluation of left ventricular dysfunction, either by ECHO or MUGA scan, at screening. Treatment discontinuation visit evaluation of LVEF does not need to be performed at treatment discontinuation visit if an evaluation has been performed within the last 12 weeks and there are no clinically significant findings and/or changes from baseline.
- ⁿ All patients will be tested for HIV prior to the inclusion into the study and HIV-positive patients will be excluded from the clinical study.
 - HBV serology will include HBsAg, total HBcAg antibody (anti-HBcAb). HBV DNA should be obtained prior to study start if patient has a negative serology for HBsAg and a positive serology for anti-HBcAb.
 - HCV serology will include HCV antibody (anti-HCV). HCV RNA should be obtained prior to study start if patient tests positive for anti-HCV.
- ^o Thyroid function testing (TSH, free T3 [or total T3 for sites where free T3 is not performed, free T4) collected at Day 1 of Cycles 1–5, and every second cycle thereafter (e.g., Day 1 of Cycles 7, 9, 11, etc.) for patients on atezolizumab only.
- ^p All women of childbearing potential will have a serum pregnancy test at screening within 14 days prior to Day 1 of Cycle 1. Urine pregnancy tests will be performed on Day 1 of every cycle and at the treatment discontinuation visit. If a urine pregnancy test is positive, it must be confirmed by a serum pregnancy test.
- ^q Includes dipstick (pH, specific gravity, glucose, protein, ketones, blood) and microscopic examination (sediment, RBCs, WBCs, casts, crystals, epithelial cells, bacteria).
- ^r Includes any medication (e.g., prescription drugs, over-the-counter drugs, herbal or homeopathic remedies, nutritional supplements) used by a patient from 7 days before initiation of study drug until 30 days after the last dose of study drug.

Appendix 1

Schedule of Activities (cont.)

- ^s After informed consent has been obtained but prior to initiation of study drug, only serious adverse events caused by a protocol-mandated intervention should be reported. After initiation of study drug, all adverse events will be reported until 90 days after the last dose of study drug or initiation of new anti-cancer therapy, whichever occurs first. After this period, all deaths, regardless of cause, should be reported. After this period, the Sponsor should be notified if the investigator becomes aware of any serious adverse event that is believed to be related to prior study drug treatment (see Section 5.6). The investigator should follow each adverse event until the event has resolved to baseline grade or better, the event is assessed as stable by the investigator, the patient is lost to follow-up, or the patient withdraws consent. Every effort should be made to follow all serious adverse events or adverse events of special interest considered to be related to study drug or trial-related procedures until a final outcome can be reported.
- ^t Archival (<5 years) or fresh baseline tumor tissue collected during screening. If a patient provides a fresh biopsy for *BRAF* test, this sample will be used also as baseline for biomarker analysis. Therefore predose specimens are not required for patients who provide a fresh biopsy before treatment start.
- If archival tissue is used availability of adequate tumor tissue must be confirmed prior to any screening procedures (paraffin-embedded tumor block or a minimum of 20 unstained slides). Submit archival tissue and associated pathology report within 30 days after Cycle 1, Day 1. If a predose fresh biopsy is collected this sample should be obtained after eligibility criteria have been fulfilled and prior to Cycle 1, Day 1. For patients who have consented to optional biopsies; an additional optional biopsy may be collected at the time of radiographic progression if clinically feasible. See Section 3.1.1 and the laboratory manual for further details.
- ^u In Cohort C, atezolizumab (1200 mg) will be given on Cycle 1, Day 1 IV Q3W. The initial dose will be delivered over 60 (\pm 15) minutes. If the first infusion is well tolerated, all subsequent infusions will be delivered over 30 (\pm 10) minutes until a loss of clinical benefit. Study drug administration may be \pm 3 days from the scheduled Day 1 of each cycle.

